### ***Confounders***

Potential confounders include the different staff inserting and caring for patients with an indwelling catheter and the indications for urinary catheterisation. The cluster randomised design of this study minimises many of these issues, as wards (clusters) act as their own control. Further, there is no reason to suggest a fundamental change in the control and intervention periods for these variables. Duration of the intervention might have a confounding effect on the outcome variables and will be accounted for in data analysis.

Clinical staff working on a casual basis or across wards have the potential to provide responses to the survey or focus group from a range of perspectives, based on their experiences on different wards. To minimise this, the survey will focus the respondent to experiences in one particular area and obtain details about their exposure to working in different wards/hospital units.

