### ***Outcomes measures***

There are two objectives for this study, (1) determining the effectiveness of the intervention and (2) the effect of the intervention on nurses' ability to deliver patient care. A summary of the objectives' key outcome measures is shown in Table 2.

Table 2. Key outcome measures

Objective 1
 
To determine the efficacy of an electronic reminder system in reducing urinary catheter usage.
	Primary outcome	1. Urinary catheter device utilization ratio (number of urinary catheter-days divided by the number of patient-days)
	Secondary outcome(s)	
1. The number of cases of catheter associated asymptomatic bacteriuria (CA-ASB) per 100 catheter days.
 
2. The number of urinary catheters inserted per 100 patient admissions

Objective 2
 
To determine whether the CATH TAG has an effect on nurses' ability to deliver patient care.
	Primary outcome	1. Perceptions of nurses about ease of use of the CATH TAG
	Secondary outcomes	
2. Perceptions of nurses about effectiveness of the CATH TAG
 
3. Changes in ownership or interest by patients in catheter management
 
4. Barriers to the CATH TAG working successfully in varied types of patients

Note: CA-ASB = catheter associated asymptomatic bacteriuria; CAUTI = catheter associated urinary tract infection

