#### Sample size:

The at risk population has been defined as patients receiving catheters in hospital. Based on pilot work, an estimated 25% of admissions will receive a catheter. We estimate that, at baseline, the median duration of catheterisation is 4 days (equivalent to a 50% probability that a catheter will be in situ on day 4). We aim to detect a difference of 20% relative risk (10% absolute risk) reduction in catheterisation on day 4, using a stepped wedge study. It is assumed the intra-ward correlation in catheter duration is  $\rho=0.1$ ). Based on pilot work it is anticipated that there will be 50 patients with a catheter per month on each ward and the study will continue for 6 months.

A power calculation was performed using the stepped wedge module in Stata. This accounts for both the clustering in outcomes by ward, as well as the paired/crossover design of the study.

At a significance level of 0.05, 2100 patients (10 wards, with 2 wards implementing the intervention at each month, forming one cluster) will be required to demonstrate a change in the probability of a catheter being in situ on day 4 from 50% to 40% with a power of 81%. Similar power would be expected with 35 patients with catheters per month in 10 wards, with two wards implementing the intervention each month (n=2100, power 81%).

*Objective 2: To determine whether the CATH TAG has an effect on nurses' ability to deliver patient care.*

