### ***Data analysis***

*Objective 1: To determine the efficacy of an electronic reminder system in reducing urinary catheter usage.*

The primary outcome measure is the duration of catheterisation, and the study aims to evaluate the effect of the intervention. The analysis will be performed using the generalised estimating equations, using the duration of catheterisation as the dependent variable and intervention as the independent variable. Duration of the intervention will be treated as a confounding variable. It is anticipated that duration of catheterisation will be normally distributed, but exploratory analyses (and where necessary transformation) will be performed. Robust standard errors will be used to adjust for correlation at ward level and autocorrelation in time. There is no expected delay in the effect of the intervention on the outcome.

*Objective 2: To determine whether the CATH TAG has an effect on nurses' ability to deliver patient care.*

Survey:

Data from the anonymous online survey will be analysed using SPSS. It is anticipated that data will be normally distributed but exploratory analyses will be performed, including testing of assumptions of linearity, homoscedasticity, multicollinearity and normality of errors and if necessary transformation of data. Validity and reliability will be examined. Subsequently a general satisfaction score and individual satisfaction scores for the four dimensions of nurses' experiences with the CATH TAG (Ease of use, Effectiveness, Changes in ownership, Barriers) will be calculated. Regression analysis will be conducted to determine if the duration of the intervention or the ward nurses primarily work on had an effect on nurses' experiences with the CATH TAG.

Any problems reported in the open questions will be taken into the focus group to be discussed and subsequently analysed qualitatively (see below).

Focus group:

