- It is impracticable to obtain consent for a number of reasons:
  - Urinary catheters are inserted in a variety of settings within a hospital. It would not be possible for researchers to determine or access patients (participants) who are about to receive a catheter. Similarly, urinary catheters are inserted by clinicians (nurses and

medical doctors) at any time of the day, it is not possible for all staff involved in catheterisation to be reached.

- Obtaining consent would require researchers to have access to a higher level of patient history and personal data.
- The clinician obtains consent for the insertion of a catheter, as part of usual medical treatment/processes, following local hospital policy.
- Urinary catheters are often inserted at a time where the patient (participant) requires urgent medical or surgical attention. Obtaining consent related to this study may delay the insertion of a catheter, compromising patient (participant) harm and increasing the risk of harm to patients.
- Retrospective consent, i.e. an approach that would result in the researchers retrospectively contacting participants to seek permission to access their medical records would raise the following ethical issues:
  - There would be considerable loss of participants included in the study as there is no system in place to identify which patients had a catheter inserted while in hospital. As such, the research could not be conducted. If a system were established, it would be administrative in nature. Further it would require the researchers to have access data of potential participants so they could be contacted. These details would include data such as names and postal addresses – information the researchers are not required to have as part of the proposed study design.
  - There would be the risk of contacting patients who underwent significant harm whilst in hospitals, suffered a traumatic event or may have passed away. The process of acquiring informed consent retrospectively would potentially result in increased harm for those participants.
- There is no known or likely reason for thinking that participants would not have consented if they had been asked as there is no risk involved and no patient intervention.
- The clinician will be following local hospital policy regarding the insertion of a catheter.
- There is no variation of care, rather an addition to existing policies, unless contra-indicated.

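### Efficacy is judged on catheter duration among catheterised patients only, although the roll-out could change who is catheterised; the listed all-patient utilisation ratio should carry the conclusion

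*Protocol*

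**What the plan says.** - **Outcomes measures, Table 2 (and Synopsis).** The primary outcome of Objective 1 is given as "Urinary catheter device utilization ratio (number of urinary catheter-days divided by the number of patient-days", a measure over all ward patients. A secondary outcome of the same objective is "The number of urinary catheters inserted per 100 patient admissions".
- **Data analysis, Objective 1.** Here the plan states: "The primary outcome measure is the duration of catheterisation, and the study aims to evaluate the effect of the intervention". The model is a GEE "using the duration of catheterisation as the dependent variable and intervention as the independent variable". The Synopsis describes the same model. No analysis of the utilisation ratio is given.
- **Sample size.** "The at risk population has been defined as patients receiving catheters in hospital". Power is computed for the probability that a catheter is still in place on day 4, 50% against 40%.
- **Confounders.** Two potential confounders are named: the staff involved and "the indications for urinary catheterisation". Both are then set aside because wards act as their own control and because "there is no reason to suggest a fundamental change in the control and intervention periods for these variables".
- **Randomisation and blinding; Implementing the intervention.** Wards are unblinded. Roll-out comes with information sessions, posters, leaflets and nurse training.
- **Data collection, Table 3.** Patient data are collected on catheterised patients. The table lists neither the indication for the catheter nor patient-days or admissions per ward.

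**The concern.** A duration exists only if a catheter is inserted, and after crossover that insertion takes place on a ward that already knows about the intervention. The analysed group is therefore formed after exposure. The trial itself asks whether insertions change, and the Background says that catheters are often placed without need, so there are insertions that could be avoided. If the marginal ones are avoided, the mix of indications among the remaining catheters changes at crossover, within each ward. Neither the ward acting as its own control nor a period term removes that.

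At stake is how the main efficacy result is read. A smaller or null difference in duration could coexist with a real fall in catheter-days, and a shorter mean duration could come from extra short reinsertions. The stability assumption is not checked, and Table 3 collects no indication with which to check it.

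**Working it through.** **Plan's own figure first.** Sample size gives 10 wards, 2 per step, 6 months, 35 catheterised patients per ward-month (10 × 6 × 35 = 2100), intra-ward correlation 0.1, alpha 0.05 (two-sided assumed), 50% against 40%. The Hussey-Hughes variance is I·s(s + T·t) / [(I·U − W)s + (U² + I·T·U − T·W − I·V)t]. Here s is the within-ward variance divided by 35, t is the between-ward variance, I = 10, T = 6, U = 30, W = 220 and V = 110. The two brackets are therefore 80 and 280.

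- Total variance 0.4 × 0.6 = 0.24, correlation 0.1: s = 0.216/35 = 0.00617, t = 0.024, SE = 0.0358, 0.10/SE = 2.79, power 79.7%.
- 0.1 read as a coefficient of variation (t = 0.05² = 0.0025, s = 0.2475/35): SE = 0.0351, power 81.3%.

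The stated 81% is reproduced to within about a point. It belongs to the day-4 probability, not to the duration model and not to the utilisation ratio.

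**Illustration of the selection.** Assumptions that are not in the protocol: exponential durations, the share f of catheters avoided, and unchanged admissions. Planned means follow from the day-4 figures: control 4/ln 2 = 5.77 days, intervention 4/ln 2.5 = 4.37 days.

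If the shortest share f is avoided, the mean among the remaining catheters is m(1 − ln(1 − f)), and catheter-days per admission are proportional to (1 − f) times that mean.

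| Scenario | Mean, days | Change in mean vs 5.77 | Change in catheter-days per admission |
|---|---|---|---|
| Planned effect, none avoided | 4.37 | −24.4% | −24.4% |
| Random 10% avoided | 4.37 | −24.4% | −31.9% |
| 10% avoided, lasting half the average: (4.37 − 0.1 × 2.18)/0.9 | 4.61 | −20.2% | −28.1% |
| Shortest 10% avoided: 4.37 × 1.105 | 4.83 | −16.4% | −24.7% |
| Shortest 20% avoided: 4.37 × 1.223 | 5.34 | −7.5% | −26.0% |
| No effect on removal, shortest 10% avoided: 5.77 × 1.105 | 6.38 | +10.5% | −0.5% |

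A different rule, in which the avoided catheters are those lasting 2 days or less, gives similar results. With the planned effect, the mean falls 17.7% (f = 10%) or 9.4% (f = 20%). With no effect on removal and f = 10%, it rises 9.3% while catheter-days fall 1.6%.

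**Opposite direction.** Suppose each catheter is a separate record and that, per 100 catheters, 10 are removed early and replaced with total days unchanged. The mean becomes 577/110 = 5.25 days, a 9.1% fall with no reduction in catheter-days.

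**Where the sign would change.** With the planned effect, mean duration shows no difference when 1 − ln(1 − f) = 5.77/4.37, that is f = 27.5%. Under the 2-day rule it is about 29%.

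**The case against.** The case against is substantial, and most of it limits the size rather than the existence of the problem.

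- **Insertion may hardly change.** The tag is attached after insertion. The ethics section says that catheters will be inserted whether or not patients are in the study and that clinicians follow local policy. The training concerns use of the tag. This stands: any effect on insertion would have to come through awareness, and the protocol gives no figure for it.
- **Avoiding the shortest catheters is a worst case.** In the model the shortest 10% last under 4.37 × 0.105 = 0.46 days, about 11 hours, and the shortest 20% under about 23 hours. The first group would be out before any red phase, whether that begins at 20 hours (Intervention) or 24 hours (Background). Catheter-days are also estimated from dates. This stands, so the table shows a range and not a forecast.
- **The Confounders sentence is not about the insertion rate.** It concerns staff and indications. A reader might infer that the trial expects the catheterised population to change and so contradicts itself. Measuring insertions does not imply that, and the stated hypothesis is one of no difference. The link is an inference: fewer marginal insertions would alter the mix of indications.
- **A reader might infer that the planned effect would vanish and power collapse.** If 20% of catheters are avoided, all of them short, the day-4 probability becomes 0.40/0.80 = 0.50. But day 4 appears only in the sample-size section. The stated analysis is of duration, which still falls 7.5% in that case. The documents do not support a claim of no visible effect, or a particular loss of power, for the primary analysis.
- **Table 2 already covers it.** The listed ratio and insertion rate would help to interpret a null duration result. This stands as a reason why the remedy is simple. It does not remove the problem while Data analysis names duration as primary and leaves the ratio without an analysis.

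**Conclusion.** The point holds in a limited form. The stated efficacy analysis is conditional on insertion, insertion is itself an outcome of the same objective, and stable indications are assumed without a check. The duration contrast could therefore be diluted or exaggerated, and the direction is not known in advance. In the illustration, dilution runs from none (random subset) through 24% to 20% (avoided 10% lasting half the average) to 24% to 16.4% or 7.5% (shortest 10% or 20%). A reversal with the planned effect present would need nearly 30% of catheters avoided. With no effect on removal, avoiding the shortest 10% would show mean duration about 10% longer while catheter-days barely move.

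These sizes rest on exponential durations and assumed avoidance shares; the protocol gives neither. The issue matters beyond the mismatch between Table 2 and Data analysis because settling that mismatch in favour of duration would leave it in place. It should be corrected before analysis, but it does not show that the trial's result would be wrong.

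**What to change.** 1. Reconcile the Synopsis, Sample size and Data analysis sections with Table 2 by making the primary analysis the listed utilisation ratio, catheter-days per patient-day by ward and period.
2. Add patient-days and admissions per ward and period to Table 3. The ratio and the insertion rate need these denominators.
3. Keep duration among catheterised patients as a supportive analysis, labelled conditional on insertion and read beside insertions per 100 admissions. State whether a reinsertion counts as a new record.
4. Remove the Confounders sentence as a justification for comparability.
5. Optionally, record whether the catheter was placed before arrival on the ward and repeat the duration analysis in those catheters. Exclude any placed on a ward that has already crossed over, since patients transfer between wards. Because information sessions reach the hospital more widely, theatre and emergency are not certain to be unaffected. This is a sensitivity analysis only, and a less precise one.

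Cost: a small amount of aggregate ward data, wording changes, and a power statement recomputed for the utilisation ratio, since the 81% does not apply to it.

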### ***Outcomes measures***

There are two objectives for this study, (1) determining the effectiveness of the intervention and (2) the effect of the intervention on nurses' ability to deliver patient care. A summary of the objectives' key outcome measures is shown in Table 2.

Table 2. Key outcome measures

Objective 1
 
To determine the efficacy of an electronic reminder system in reducing urinary catheter usage.
	Primary outcome	1. Urinary catheter device utilization ratio (number of urinary catheter-days divided by the number of patient-days)
	Secondary outcome(s)	
1. The number of cases of catheter associated asymptomatic bacteriuria (CA-ASB) per 100 catheter days.
 
2. The number of urinary catheters inserted per 100 patient admissions

Objective 2
 
To determine whether the CATH TAG has an effect on nurses' ability to deliver patient care.
	Primary outcome	1. Perceptions of nurses about ease of use of the CATH TAG
	Secondary outcomes	
2. Perceptions of nurses about effectiveness of the CATH TAG
 
3. Changes in ownership or interest by patients in catheter management
 
4. Barriers to the CATH TAG working successfully in varied types of patients

Note: CA-ASB = catheter associated asymptomatic bacteriuria; CAUTI = catheter associated urinary tract infection

**Definitions**

CA-ASB is defined as the presence of  $\geq 10^5$  colony forming unit (cfu)/ml of  $\geq 1$  bacterial species in a single catheter urine specimen in a patient without symptoms compatible with UTI (Hooton et al., 2010).

[figure not shown]

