## ***Data collection***

*Objective 1: To determine the efficacy of an electronic reminder system in reducing urinary catheter usage*

Data will be collected by a specific staff member at the hospital, supported by the research team. Where data collection results in an increase in workload for the hospital staff (e.g. not part of usual practice), the research team will provide additional resources in the form of funding to account for additional hours for existing staff members or employment of new staff members for the purpose of data collection. The research team will provide the hospital staff member(s) with training about the project, data collection processes and data collection tools, as well as ongoing on-site and telephone support. For the purpose of this protocol, the dedicated hospital staff member(s) will be referred to as hospital personnel.

The figure below (Figure 2) summarises the data collection process with further details provided below.

*Figure 2.* Overview of the data collection process

Hospital personnel will prospectively collect data five days a week on participating hospital wards, during both control and intervention periods. Hospital personnel will visit inpatient areas and patients who receive an indwelling urinary catheter will be identified and followed-up until discharge or catheter removal. Hospital personnel will check that a CATH TAG has been attached to every catheter, on wards that have crossed over to the intervention. The following information will be collected: hospital number, age, sex, date of admission, date and time of catheter insertion, reason for censoring follow-up, date of discharge or catheter removal, designation of person

inserting the catheter, ward and allocation to control or intervention ward. A review of microbiology results will be undertaken by the hospital personnel for each person who receives a catheter and has a urinary sample taken. If a person has a positive urine culture after catheterisation and prior to removal, the following will be collected: data of specimen collection, organism(s) isolated, colony forming units, white cell count.

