Table 3 outlines the data to be collected, data sources and timing of data collection. The number of catheter days for each patient included in the study will be estimated from the date of catheter insertion to the date of removal. Hospital personnel will record all captured data locally, on a spreadsheet designed by the research team specifically for the purpose of the trial.

Table 3. Types, sources and timing of data collection

Data collected	Source	Collected by	Timing	Used for
Details of patient who received a catheter:				

 
Hospital number
 
	Medical notes	Hospital personnel	Control and intervention periods	Link to laboratory data

 
Date of birth
 
	Medical notes	Hospital personnel	Control and intervention periods	Data analysis

 
Sex
 
	Medical notes	Hospital personnel	Control and intervention periods	Data analysis

 
Date of admission
 
	Medical notes	Hospital personnel	Control and intervention periods	Data analysis

 
Date and time of catheter insertion
 
	Medical notes	Hospital personnel	Control and intervention periods	Calculating catheter days Data analysis

 
Date and time of catheter removal
 
	Medical notes	Hospital personnel	Control and intervention periods	Calculating catheter days Data analysis

 
Reason for censoring follow-up (discharged, catheter removal, transfer from control to intervention wards or vice versa)
 
	Medical notes	Hospital personnel	Control and intervention periods	Data analysis
Additional information required:				

 
Designation of person inserting
 
	Medical notes	Hospital personnel	Control and intervention periods	Data analysis

catheter			periods	
• Ward		Hospital personnel		
• Intervention/Control Allocation		Hospital personnel		
Laboratory result of any patient who received a catheter:				
• Has a catheter urine sample been taken (Y/N)	Microbiology laboratory	Hospital personnel	Control and intervention periods	Data analysis
If catheter urine sample has been taken:				
• Date of specimen collection	Microbiology laboratory	Hospital personnel	Control and intervention periods	Data analysis

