• Species isolated	Microbiology laboratory	Hospital personnel	Control and intervention periods	Defining the outcome
• Colony count and white cell count where appropriate / provided	Microbiology laboratory	Hospital personnel	Control and intervention periods	Defining the outcome

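### The CA-ASB outcome requires absence of UTI symptoms, but no listed data item records symptoms and no study specimen is scheduled

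*Protocol*

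**What the plan says.** The Synopsis and Table 2 (Protocol, Outcomes measures) list as the first secondary outcome of Objective 1 "The number of cases of catheter associated asymptomatic bacteriuria (CA-ASB) per 100 catheter days". The Definitions section gives a case two elements. One is microbiological: at least 10^5 cfu/ml of one or more species. The other is clinical: the growth must be found "in a single catheter urine specimen in a patient without symptoms compatible with UTI".

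Under Data collection, Objective 1, microbiology results are reviewed "for each person who receives a catheter and has a urinary sample taken". If a culture is positive between catheterisation and removal, "the following will be collected: data of specimen collection, organism(s) isolated, colony forming units, white cell count". Table 3 adds a yes/no item for whether a catheter urine sample was taken. In its column on what each item is used for, only two rows are marked as defining the outcome: species isolated, and "Colony count and white cell count where appropriate / provided". The Ethics section on catheter data describes the study as gathering data that already exist, and no section schedules a urine specimen for study purposes.

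**The concern.** A two-part definition needs data on both parts. The laboratory part is collected. The clinical part, which distinguishes asymptomatic bacteriuria from symptomatic infection, has no matching item. If the plan is carried out as written, the report will call an outcome asymptomatic without a recorded basis for doing so.

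Ascertainment adds a second difficulty. Asymptomatic bacteriuria can be found only by culturing urine, and here urine is cultured only if someone chose to send it. The count therefore depends on sampling practice as well as on bacteriuria. Wards are unblinded (Randomisation and blinding). They also receive information sessions and training before crossover (Implementing the intervention), so the outcome has no protection if sampling practice shifts at that point.

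**Working it through.** The protocol states no CA-ASB rate, effect size or power, so there is no figure to reproduce. The check sets the definition beside the data items and then illustrates scale.

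**Definition against data items**

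| Element of the definition | Item in the Data collection text or Table 3 |
|---|---|
| Catheter urine specimen | Sample taken (yes/no); specimen date |
| One or more bacterial species | Species isolated |
| At least 10^5 cfu/ml | Colony count, where provided |
| No symptoms compatible with UTI | None |

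The remaining items are hospital number, age or date of birth, sex, admission date, catheter insertion and removal, reason for censoring, designation of the inserter, ward and allocation. None records fever, urinary symptoms, a UTI diagnosis or the indication for the specimen. The white cell count is a laboratory value and does not record symptoms.

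**Scale of possible symptomatic cases.** Background gives a 1% CAUTI risk among catheterised patients. Sample size gives 2100 patients, or 50 × 10 wards × 6 months = 3000 at the anticipated throughput.

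- 2100 × 0.01 = 21
- 3000 × 0.01 = 30

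The listed items give no means of removing from the CA-ASB count those of these patients who have a qualifying culture.

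**Direction of error.** Let c be the risk of symptomatic infection (1%, from Background), a the true risk of asymptomatic bacteriuria, and q the chance that an asymptomatic case is sampled. Both a and q are assumptions. Assume also that every symptomatic patient is sampled and culture-positive. Then

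- counted cases = c + a·q
- symptomatic share of counted cases s = c / (c + a·q)

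| a | q | Counted per 100 patients | True asymptomatic per 100 | s |
|---|---|---|---|---|
| 2% | 10% | 1.2 | 2 | 83% |
| 2% | 100% | 3.0 | 2 | 33% |
| 5% | 10% | 1.5 | 5 | 67% |
| 5% | 100% | 6.0 | 5 | 17% |
| 10% | 10% | 2.0 | 10 | 50% |
| 10% | 100% | 11.0 | 10 | 9% |

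The counted figure lies below the true one in three rows and above it in three. Dividing both by the same catheter days does not change that.

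**Comparison between periods.** Rearranging, the counted risk equals a·q / (1 − s). With subscripts 0 for control and 1 for intervention, the counted ratio is

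(a1/a0) × (q1/q0) × (1 − s0)/(1 − s1).

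If q and s are the same in both periods, the last two factors equal 1 and the true ratio is recovered. If they change, the effect depends on which patients are sampled. With a = 5% and c = 1% unchanged, let q rise from 10% to 12%, a 20% relative increase:

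- counted before: 0.01 + 0.05 × 0.10 = 0.015
- counted after: 0.01 + 0.05 × 0.12 = 0.016
- ratio: 0.016 / 0.015 = 1.067, an apparent rise of about 7% with no true change

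**The case against.** The strongest reply has four parts.

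- **Staff could apply the criterion themselves.** Hospital personnel visit the wards and use the medical notes, so they could judge symptoms when recording a case. They could, but the protocol does not say that they will, and it gives them nowhere to record the judgement.
- **A figure may contain the step.** Two figures are not shown, one directly after the definition and one on the data collection process. A symptom check there cannot be excluded. However, the process figure is described as a summary of the text, and Table 3 is presented as the outline of what is collected; neither the text nor Table 3 has such an item.
- **The analysis plan may deal with it.** That plan is not at hand, but no analysis can apply a criterion for which no data were recorded.
- **Each ward is its own control.** A constant sampling rate and symptomatic share would cancel in the comparison. This stands, and it limits the finding.

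A reader might also infer stronger claims that the documents do not support.

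- That any bacteriuria is counted: the colony count is collected, so the 10^5 threshold can be applied wherever the laboratory reports one.
- That CA-ASB is over-counted by a factor 1/(1 − s): this compares only with asymptomatic cases that were sampled and ignores those that were not.
- That a 20% change in sampling moves the outcome by 20%: this needs the additional samples to be positive as often as the existing ones.
- That specimens are mostly sent for suspected infection: the documents do not say who requests them or why.

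**Conclusion.** The point holds as a mismatch between a definition and its data. The symptom element of CA-ASB has no listed item, and the laboratory items alone are marked as defining the outcome. The counted quantity is bacteriuria at the threshold among patients who happened to be sampled. It may include symptomatic infection, with about 21 to 30 such infections expected at the protocol's own 1% risk, and it misses asymptomatic cases that were never cultured. Its net direction against true CA-ASB incidence is unknown.

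The meaning of the absolute rate is affected in any case. Bias in the comparison of control and intervention periods needs a change in sampling or in the symptomatic share at crossover. The protocol gives no evidence of such a change: the device prompts review of the catheter, not urine collection. This is a possible risk, not a demonstrated bias.

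The conclusion rests on the visible text and Table 3 being complete, and on reading unscheduled specimens as taken in routine care, which the documents imply but do not state. It concerns one secondary outcome. The primary outcome and the sample size are unaffected.

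**What to change.** Choose one of two changes.

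- **Keep the outcome.** Add one field to Table 3 and to the Data collection text, completed for positive cultures only: symptoms compatible with UTI documented, Y/N. Count as CA-ASB only the positive cultures without documented symptoms.
- **Keep the data.** Rename the outcome *catheter-associated bacteriuria (at least 10^5 cfu/ml) in specimens taken in routine care* in the Synopsis, Table 2 and Definitions.

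In either case, report the proportion of catheterised patients sampled in control and intervention periods, using the yes/no item already in Table 3. A reader can then see whether sampling shifted at crossover.

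The first change costs one chart item per positive culture, recorded by staff who already use these patients' notes. Renaming needs no new data, but it is not free: either route is a protocol amendment, which the Ethics section sends to the HREC. Neither route recovers asymptomatic cases that were never cultured, so the report should state that limit.
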